9 CHANGES FROM THE PROTOCOL SPECIFIED STATISTICAL ANALYSIS

- Statistical analysis for the QSU-brief questionnaire data and the mCEQ questionnaire data will be performed including interaction terms for arm and time point to enable least square means to be calculated at each time point in order to explore the pattern of the CHTP 1.2 effect over time. The main comparison between arms will be the comparison over all of the time points.

Reason for change:

This analysis would capture the evolution of perception of the product and the adaptation process taking into account the subjects' repeated measurements.

- The descriptive statistics of the biomarkers of the primary endpoints will also be calculated per stratification factor.

Reason for change:

The protocol specified that primary endpoint analyses would be done by stratification factor, and this clarifies that descriptive statistics will also be presented by stratification factor.

- The summary of demographics will also be performed on the FAS.

Reason for change:

If the safety population differs from the FAS, then a summary of the demographics for the FAS is also required.

- The categorisation of the SES questionnaire into low, moderate and high SES will not be performed.

Reason for change:

There is no scoring algorithm available for the Socio-Economic Status questionnaire in the study population.

- The number and percentage of subjects with clinical findings will not be tabulated by sequence for laboratory parameters.

Reason for change:

No sequence occurred in this study. The tabulation will be done by arm. The error is corrected in this Analysis Plan.

- The endpoint "Ratio of 8-epi-prostaglandin F2 α (8-epi-PGF2 α) to prostaglandin F2 α (PGF2 α)" will only be listed.

Reason for change:

During the course of the study, the most recent development of the assay to measure the 8-epi-PGF2 α to PGF2 α ratio showed that the ratio is not an effective endpoint for the

determination of oxidative stress. The collection of samples and the analysis for this endpoint was stopped and the results will only be listed in the Clinical Study Report.

- The definition of the Quitters population was added in section **10.7 Quitters Population**.

Reason for change:

The purpose of this addition was to clarify the population on which exploratory endpoint 4 will be assessed.

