12.5.2.1.3 NEQ

NEQ will be expressed as concentrations adjusted for creatinine and as the quantity excreted over 24 hours. It will be assumed that NEQ is log-normally distributed.

The values and percent changes for NEQ in the quantity excreted over 24-hours and the concentration adjusted for creatinine will be listed and summarized (Table 15.2.4.13.X and Listing 15.3.3.1). In addition line graphs will be produced for arm geometric means (and 95% CI) over all timepoints (Figure 15.1.2.26 and 15.1.2.27).

The analysis will compare the log-transformed NEQ between the CHTP 1.2 and CC arms on Day 5 and Day 90 Visit. The statistical model and SAS code will be the same as described in Section 12.5.1.1 “Primary endpoints” (Table 15.2.4.1).

In addition, a repeated measures mixed model on the log-transformed NEQ will be used with terms for log-transformed baseline, sex, average daily CC consumption over the last 6 weeks as reported during admission, arm, timepoint, and the interaction between arm and timepoint. The interaction term will be removed if $p > 0.1$.

The SAS code to be used is shown below:

```
Proc mixed data=_data_ method=REML;
Class arm sex cigarette_cons time_point_cat subject period;
Model log(NEQ) = log(base) sex period cigarette_cons arm
arm*time_point time_point;
Repeated time_point_cat / subject=subject type=un;
Lsmean arm / diff alpha=0.05 cl;
Run;
```

The least squares (LS) means and estimate of the difference along with its 95% CI will be back-transformed before presenting in the tables. The geometric LS means for each arm along with the reduction (i.e: 100% - ratio of CHTP 1.2 : CC (%)) and 95% CI will be presented in Table 15.2.4.14. This will be done for all individual timepoints. If the interaction term is present in the model, the reduction will also be shown for the individual timepoints.

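### The NEQ repeated-measures code, reused for nicotine, cotinine and mCEQ, does not produce the per-timepoint arm comparisons that its text promises

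*SAP*

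**What the plan says.** The text of SAP 12.5.2.1.3 lists log baseline, sex, cigarette consumption, "arm, timepoint, and the interaction between arm and timepoint", with the interaction dropped if p > 0.1. Of the back-transformed LS means, reduction and confidence interval it says "This will be done for all individual timepoints", and then "If the interaction term is present in the model, the reduction will also be shown for the individual timepoints".

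The code given as the code to be used reads:
- CLASS statement: "Class arm sex cigarette_cons time_point_cat subject period"
- MODEL statement: "Model log(NEQ) = log(base) sex period cigarette_cons arm", continuing with "arm*time_point time_point"
- REPEATED statement: indexed by `time_point_cat`, unstructured covariance
- LS means: "Lsmean arm / diff alpha=0.05 cl"

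Section 12.5.2.2 applies this model to plasma nicotine and cotinine. Section 12.5.3.1.2 applies the code to mCEQ and says each post-baseline timepoint will be compared. Section 9 explains that QSU-brief and mCEQ are analysed "including interaction terms for arm and time point to enable least square means to be calculated at each time point", and that the main comparison is the one over all time points.

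**The concern.** Text and code disagree in three places.

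1. **Time variable.** `time_point_cat` is classified and used in REPEATED, but MODEL contains `time_point`, which is not in CLASS. PROC MIXED treats it as numeric, so time and arm-by-time each have one degree of freedom.
2. **Extra term.** `period` is in MODEL but not in the text's list.
3. **LS means.** Only arm is requested, with no arm-by-time term and no AT option. The output is one LS mean per arm and one difference.

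NEQ, nicotine and cotinine are the endpoints of secondary objective 4, which concerns levels over the whole exposure period. The purpose stated for mCEQ is to follow how the effect changes as subjects adapt. Run as printed, the code would not provide that. The p > 0.1 rule would also test a single slope rather than a factor-by-arm interaction.

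**Working it through.** The SAP gives no figure to reproduce here, so the check is of structure, followed by an illustration with assumed profiles.

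**Timepoints.** NEQ and mCEQ have 8 post-baseline timepoints: Days 1–5, 30, 60 and 90. Nicotine and cotinine have a ninth if the Day 6 morning sample (SAP Table 14) is included. There are 4 product use periods, with Days 1–5 all in period 1.

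**What the coded mean model allows.** Period plus a common slope gives a shared profile of rank 5 over 8 timepoints. Because `period` is common to both arms, it leaves the arm difference on the log scale as intercept + slope × `time_point`: two parameters, against eight with categorical time. The interaction test has 1 df instead of (2−1)×(8−1) = 7, or 8 with nine timepoints.

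**Where the single LS mean is evaluated.** `LSMEANS arm` is taken at the mean of `time_point`.
- Study-day coding, complete data: (1+2+3+4+5+30+60+90)/8 = 195/8 = 24.4 days.
- Study-day coding, with 40 of 80 CHTP subjects missing at Days 30–90: (120×15 + 80×180)/(120×5 + 80×3) = 16,200/840 = 19.3 days.

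No measurement is scheduled on either day.

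**Illustration (assumed profile, flat CC).** True ratios are 0.60, 0.70, 0.80, 0.90, 1.00 on Days 1–5, then 1.00. Take independent errors and complete data first, where the fit is an ordinary line through the log ratios.
- Mean log ratio: (−0.5108 − 0.3567 − 0.2231 − 0.1054)/8 = −0.1495, so the overall ratio is e^−0.1495 = 0.86.
- Sxx = 12,655 − 195²/8 = 7,901.9; Sxy = 26.84; slope = 26.84/7,901.9 = 0.00340 per day.
- Day 1: exp(−0.1495 + 0.00340×(1 − 24.375)) = 0.80 (true 0.60).
- Day 5: exp(−0.1495 + 0.00340×(5 − 24.375)) = 0.81 (true 1.00).
- Day 90: exp(−0.1495 + 0.00340×(90 − 24.375)) = 1.08 (true 1.00).

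The same fit was run by generalised least squares with 80 CHTP and 40 CC subjects. It used five working correlations (independence; compound symmetry 0.5 and 0.8; AR(1) 0.5 and 0.8), each with complete data and with half the CHTP ambulatory data missing. Ranges over the 10 cases:

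| | True | Study-day coding | 1–8 coding |
|---|---|---|---|
| Day 1 | 0.60 | 0.77–0.80 | 0.63–0.67 |
| Day 5 | 1.00 | 0.78–0.81 | 0.85–0.90 |
| Day 90 | 1.00 | 0.89–1.08 | 1.05–1.13 |

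The overall arm ratio is 0.80–0.86 against a true 0.86. An arm effect that really is linear on the coded scale is recovered without error.

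**Interaction rule.** With an assumed log-SD of 0.6, complete data, and noncentral chi-square at 0.10, the chance of keeping the interaction is:
- Dip (1.00, 0.80, 0.80, 0.90, 1.00, then 1.00): 0.10–0.88 with the slope test, 0.47–0.99 with 7 df.
- Step (0.80 on Days 1–5, then 1.00): 0.48–1.00 with the slope test, 0.47–1.00 with 7 df.

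**Is restoring `_cat` enough?** No. With categorical time, each timepoint determines its period. Default LS means weight the four periods equally, and those combinations are not estimable. A rank check confirms that with `period` kept, no arm or arm-by-time LS mean is estimable, although the arm differences are. With `period` removed, all of them are.

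**The case against.** The NEQ text never says that timepoint is categorical, and two differently named variables could mean a deliberate numeric trend with a categorical copy for REPEATED. The SAP's snippets are also schematic (`Lsmean` for `LSMEANS`, `log()` inside MODEL), so a programmer would rewrite them, guided by prose that states the intended output. The planned figure of mCEQ LS mean differences could not be filled from a single difference, so the gap would surface in production. The reach is secondary or exploratory, descriptive means by timepoint are planned anyway, and the profiles used above are assumed.

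Much of this stands as a limit on importance. The illustrated sizes show what could happen under verbatim execution and do not predict harm. It does not rescue the code. Even if numeric time was intended, an arm-only LS means request without an AT option cannot give results at individual timepoints. The SAP's own cough model does request arm-by-visit LS means. A dropped `_cat`, the likely cause of the first mismatch, explains neither the LS means line nor `period`. Three statements would need changing without written authority.

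**Conclusion.** The concern holds. The printed code contradicts the section's text and cannot deliver the per-timepoint LS means and reductions described for NEQ, nicotine, cotinine and mCEQ. That conclusion needs no assumption about the data.

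The size of any distortion depends on the time coding, which the SAP does not state, and on the true profile, which is unknown. It ranges from nothing for a linear effect to a fitted 0.78–0.81 where the truth is 1.00 in the example. The interaction rule can shift in either direction.

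This should be corrected, but its reach is limited to secondary objective 4 and exploratory mCEQ. The primary analyses and the NEQ ANCOVAs at Day 5 and Day 90 stand, and the comparison over all time points is much less affected.

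**What to change.** Amend SAP 12.5.2.1.3 before database lock:

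- **MODEL:** log value on log baseline, sex, `cigarette_cons`, arm, `time_point_cat` and `arm*time_point_cat`. Keep REPEATED on `time_point_cat` with unstructured covariance.
- **Remove `period`.** The text does not list it, and keeping it with categorical time makes the LS means non-estimable. The period-specific per-protocol rule in 12.1.7 can be applied by selecting records.
- **LSMEANS:** request arm and `arm*time_point_cat`, with arm differences at each timepoint.
- **mCEQ:** state that it uses this code without the log, since 12.5.3.1 plans the natural scale.
- **QSU-brief (a separate slip):** 12.5.3.1.1 refers to a repeated-measures model in 12.5.1.1, which contains only an ANCOVA. Point it to this code, without the log.

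The cost is a few lines of SAP code and 7 − 1 = 6 extra interaction degrees of freedom (8 − 1 = 7 for nicotine and cotinine if Day 6 is included), which is small with about 120 subjects.

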12.5.2.2 Nicotine and Cotinine Concentrations

It is assumed that Nicotine and Cotinine concentrations are log-normally distributed.

The descriptive analysis will be the same as described in Section 12.5.1.1 “Primary endpoints”.

The percent change from baseline will be calculated. The concentrations of nicotine and cotinine will be listed and summarized along with this change (Table 15.2.4.15 and Listing 15.3.4.1). Line graphs of the nicotine and cotinine concentration profiles across all study days showing geometric mean and 95% CI will also be produced (Figure 15.1.2.28).

Nicotine and cotinine values will also be analyzed in a repeated measures mixed model on the log-transformed values, as described in section “12.5.2.1.3 NEQ” (Table 15.2.4.16).

12.5.2.3 CYP1A2 Activity

It is assumed that CYP1A2 Activity is normally distributed.

Descriptive statistics of the values and change from baseline and supportive listings will be provided (Table 15.2.4.17 and Listing 15.3.3.1).

The analysis will compare the Day 5 and Day 90 Visit values between the CHTP 1.2 and CC arms. An ANCOVA model will be used with terms for sex, average daily CC consumption over the last 6 weeks as reported during admission and arm. The SAS code will be the same as described in Section 12.5.1.1 “Primary endpoints”; but then without a log-transformation.

The least squares (LS) means and estimate of the difference along with its 95% CI will be presented in the tables (Table 15.2.4.18).

12.5.2.4 Spirometry

Spirometry parameters assessed during the study include:

- Measured forced expiratory volume in 1 second (FEV₁)
- Measured forced vital capacity (FVC)
- FEV₁/FVC
- Percent of predicted FEV₁ (% pred)
- Percent of predicted FVC (% pred)
- Measured FEF 25 - 75
- Measurement interpretation (categories: normal, abnormal, abnormal clinically significant)

The above data are collected at Screening, Day 6, and Day 90 Visit. At Screening, data are collected at least one hour after having stopped smoking. On Day 6 and Day 90 Visit, spirometry has to be done prior to smoking.

It is assumed that these parameters are normally distributed.

Spirometry data values and normal/abnormal will be listed by arm and study day (Listing 15.3.4.3). Assessments performed after baseline will be listed together with change from

baseline and shift in normality. Spirometry data from subjects who had significant clinical findings will be highlighted in listings.

Descriptive statistics will be presented for FEV₁(L), FEV₁ (% pred), FVC(L), FVC(% pred), FEV₁/FVC, FEF (measured) at baseline, on Day 6 and at Day 90 Visit by arm, and overall for the safety population and for the PP population. Spirometry data will be summarized together with changes from baseline for data with and without bronchodilator (Table 15.2.4.19.x). The number and percentage of subjects with normal/abnormal/abnormal clinically significant results will be presented in Table 15.2.4.20.X.

For the PP population, the analysis will compare the Day 6 and Day 90 Visit values between the CHTP 1.2 and CC arms. An ANCOVA model will be used with terms for sex, average daily CC consumption over the last 6 weeks as reported during admission and arm. The SAS code will be the same as described in Section 12.5.1.1 “Primary endpoints”; but then without a log-transformation.

The least squares (LS) means and estimate of the difference along with its 95% CI will be presented in the tables. The LS means for each arm along with the difference and 95% CI will be presented in the table (Table 15.2.4.21).

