**Table 14: Assessment Windows**

Assessment	Nominal Time point(s)	Window
	Day 30 Visit, Day 60 Visit and Day 90 Visit	CC arm and prior to use of the first CHTP 1.2 in the CHTP 1.2 arm. Start at 09:00 ± 30 minutes (after bladder void) until 24-hours ±1 hour later.
Spirometry	Screening Day 6 and Day 90 Visit	spirometry without bronchodilator: at least 1 hour after having stopped smoking and prior to spirometry with bronchodilator spirometry with bronchodilator performed 15-30 minutes post administration of salbutamol spirometry will be performed prior to product use (CC or CHTP 1.2). spirometry post-bronchodilator performed 15-30 minutes post administration of salbutamol Day 6: 06:29 AM ± 1.5h Day 91: prior to 11:30 AM
CYP1A2 activity	Day -1, Day 5 and Day 90 Visit	6 hours after intake of cup of coffee ± 15 min
CYP2A6 activity	Day -3, Day 6 and Day 90 Visit	Prior to smoking / product use Day -3 and Day 90 Visit (Day 91): prior to 11:30 AM Day 6: 06:29 AM ± 1.5h
CO breath test	Day -2 to Day 5 Day -3, Day 30 Visit, Day 60 Visit and Day 90 Visit	in the evening around 08:00 PM ± 1.5 hour in conjunction (i.e., within 30 minutes) with COHb tests. First day of the respective visits; irrespective of time of product use
Assessment of Cough	Day -2 to 6 Day 30 Visit, Day 60 Visit and Day 90 Visit	To be done prior to product use but not later than 11:30 AM Second day of the respective visits; prior to 11:30 AM; irrespective of time of product use
Nicotine and cotinine in plasma	Day -1 to Day 6	Day -1 to Day 5: between 08:00 PM ± 1.5 hour. Day 6: between 06:29 AM ± 1.5h.

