12.5.1.1 Primary endpoints

COHb in blood, and urinary concentrations adjusted for creatinine of MHBMA, 3-HPMA and S-PMA, and total NNAL will be summarized on the log-scale as detailed in **Section 12.1.3 “Descriptive Statistics”**. Distributions will be tested for log-normality and appropriate non-parametric methods will be used in case of non-lognormally distributed data as described in **12.1 General Considerations**.

The values and percent changes from baseline in the concentration adjusted for creatinine of MHBMA, 3-HPMA, S-PMA and total NNAL will be listed and summarized along with the COHb concentrations and percent changes from baseline (Tables 15.2.3.3-7.1, 15.2.3.3-7.2 and Listing 15.3.3.1). This will also be summarized by sex, by average cigarette consumption over the previous 6 weeks prior to admission and by product use category (Tables 15.2.3.3-7.1.1, 15.2.3.3-7.1.2 and 15.2.3.3-7.1.3).

The log-transformed data will be analyzed by means of an ANCOVA (on Day 5 for COHb, MHBMA, 3-HPMA and S-PMA and Day 90 Visit for total NNAL) using arm as covariate adjusting for sex and average cigarette consumption over the previous 6 weeks prior to admission, and log-transformed baseline value of endpoint.

The SAS code to be used for COHb in blood, and urinary concentrations adjusted for creatinine of MHBMA, 3-HPMA and S-PMA on Day 5 and total NNAL adjusted for creatinine at Day 90 Visit is shown below:

```
Proc mixed data=_data_ ;  
Class arm sex cigarette_cons ;  
Model log (Value) = log (baseline) sex cigarette_cons arm ;  
Lsmeans arm / pdiff =control('CC') alpha=0.05 cl ;  
Run ;
```

The least squares (LS) means and estimate of the difference along with its 95% CI will be back-transformed before presenting in the tables. The geometric LS means for each arm along with the reduction (i.e: 100% - ratio of CHTP 1.2 : CC (%)) and 95% CI will be presented in the tables (Table 15.2.3.1).

In addition line graphs will be produced for arm geometric means (and 95% CI) over all timepoints for COHb in blood, and urinary concentrations adjusted for creatinine of MHBMA, 3-HPMA, S-PMA and total NNAL (Figure 15.1.1.1-5).

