12.5.2 Secondary Analyses

12.5.2.1 Biomarkers of Exposure

12.5.2.1.1 Exhaled CO

CO in exhaled breath (expressed as ppm), will be measured using the Micro+™ Smokerlyzer® or similar device, conducted on Day -3 to Day 5, Day 30 Visit, Day 60 Visit and Day 90 Visit.

Descriptive statistics summarized by arm will be produced separately for all timepoints for all visits applicable for exhaled CO. Exhaled CO will be summarized on the natural scale as detailed in Section 12.1.3 “**Descriptive Statistics**”. Distribution will be tested for normality and appropriate non-parametric methods will be used in case of non-normally distributed data as described in 12.1 **General Considerations**.

Actual values and changes from baseline in levels of exhaled CO will be listed and summarized (Table 15.2.4.2.X and Listing 15.3.3.1). In addition line graphs will be produced for arithmetic means (and 95% CI) per randomization arm over all timepoints (Figure 15.1.2.5).

An ANCOVA model on exhaled CO (Day 5 and Day 90 Visit) will be used with terms for the baseline value, sex, average cigarette consumption over the previous 6 weeks prior to Admission and arm. The LS means on Day 5 and Day 90 for each arm along with the difference (CHTP 1.2 - CC) and 95% confidence interval (CI) will be presented in the tables (Table 15.2.4.1).

The statistical model and SAS code for the analysis of exhaled CO on Day 5 and at Day 90 Visit and COHb at Day 90 Visit will be the same as described in Section 12.5.1.1 “**Primary endpoints**”; except that there will be no log transformation of the data and back-transformation of the LS Means estimates of the difference.

If applicable, the table with descriptive statistics will be repeated for the group of subjects who attempt to quit (see section “**10.7 Quitters Population**”)

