12.5.3.1.1 Urge-to-Smoke Questionnaire of Smoking Urges Brief

All summaries, profiles and analysis will be presented for the CHTP 1.2 and CC arms.

The change from baseline will be calculated for the total score and the two domain scores (relief and reward). The total score and two domain scores, along with the change from baseline will be summarized (Table 15.2.5.1). The answers to the individual questions, along with the domain scores, total scores and changes from baseline will be listed (Listing 15.3.5.1).

The profiles of the arithmetic means and LS Mean differences per timepoint for the total score and two domain scores will be produced (Figure 15.1.3.1 and Figure 15.1.3.2).

The analysis will compare each post baseline timepoint in the domain and total scores. A repeated measures mixed model will be used with terms for baseline QSU-BRIEF score, sex, average daily CC consumption over the last 6 weeks as reported during admission, arm, timepoint, and the interaction between arm and timepoint. The interaction term will be removed if $p > 0.1$.

The SAS code will be the same as the repeated measures model described in Section “12.5.1.1 Primary endpoints”.

LS means for each arm along with the difference (CHTP 1.2 - CC) with 95% CI will be presented in table 15.2.5.2.

All figures, summaries and analyses will be performed on the Per Protocol Populations.

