12.5.3.2 CYP2A6 Activity

If feasible, CYP2A6 will be analyzed in natural scale.

Descriptive statistics of the values and change from baseline on Day 6 and Day 90 Visit (Table 15.2.5.9) and supportive listings will be provided (Listing 15.3.5.6).

The analysis will compare the Day 6 and Day 90 Visit values between the CHTP 1.2 and CC arms. An ANCOVA model will be used with terms for baseline, sex, average daily CC consumption over the last 6 weeks as reported during admission and arm (Table 15.2.5.10).

The SAS code will be the same as described in Section “**12.5.1.1 Primary endpoints**”.

LS means for each arm along with the difference (CHTP 1.2 - CC) and 95% CI will be presented in the tables.

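### For CYP1A2 and spirometry the SAP lists ANCOVA terms without baseline but cites code that includes it, and does not say which governs

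*SAP*

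**What the plan says.** SAP 12.5.2.3 (CYP1A2) and 12.5.2.4 (spirometry) use the same sentence for the model: "An ANCOVA model will be used with terms for sex, average daily CC consumption over the last 6 weeks as reported during admission and arm". Each goes on: "The SAS code will be the same as described in Section 12.5.1.1", with one exception, that the data are not logged. The model statement being cited, in SAP 12.5.1.1, is "Model log (Value) = log (baseline) sex cigarette_cons arm".

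Other sections use the same code and do list baseline. For exhaled CO, SAP 12.5.2.1.1 says "An ANCOVA model on exhaled CO (Day 5 and Day 90 Visit) will be used with terms for the baseline value, sex" and goes on to CC consumption and arm; it too drops only the log. The oxidative stress (12.5.2.7), FTND (12.5.3.1.4) and CYP2A6 (12.5.3.2) sections also name baseline.

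A baseline is collected for both endpoints. SAP Table 14 schedules CYP1A2 at "Day -1, Day 5 and Day 90 Visit". Spirometry is done at Screening, Day 6 and the Day 90 Visit, and SAP 12.5.2.4 already uses the Screening value descriptively: "Spirometry data will be summarized together with changes from baseline for data with and without bronchodilator". Table 17 of the SAP defines baseline as the last valid value before first product use in the exposure period.

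**The concern.** Taking the logs out of the cited code leaves baseline in the model, so the prose and the code give different analyses of the same endpoint. A programmer and an independent checker could each follow the SAP and report different intervals, and possibly different estimates.

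Omitting baseline would lose precision on two secondary endpoints whose objectives are about change. In the Day 90 per-protocol set, any baseline difference between the retained CHTP 1.2 subjects and the CC arm would also carry into the unadjusted comparison. The study statisticians are unblinded at the later of SAP finalisation and database lock (SAP 6.3.2), so an unresolved choice could be made with the arms in view.

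**Working it through.** **Text against code**

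| Section | Terms listed in prose | Terms in the cited code, log removed where stated |
|---|---|---|
| 12.5.2.3 CYP1A2 | sex, CC consumption, arm | baseline, sex, CC consumption, arm |
| 12.5.2.4 Spirometry | sex, CC consumption, arm | baseline, sex, CC consumption, arm |
| 12.5.2.1.1 Exhaled CO | baseline, sex, CC consumption, arm | same as prose |

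The first two rows differ by exactly the baseline term.

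**Does anything settle it?** No rule gives text or code precedence. Protocol 12.4.4 specifies baseline adjustment for biomarkers of exposure only and has no CYP1A2 or spirometry model. All five ANCOVAs elsewhere that list their terms (primary endpoints, exhaled CO, oxidative stress, FTND, CYP2A6) include baseline, which points to the code. The SAP's pointers to this code are not fully reliable, however. For QSU-brief, 12.5.3.1.1 says "The SAS code will be the same as the repeated measures model described in Section" and then names 12.5.1.1, which contains no repeated-measures model. For CYP2A6, 12.5.3.2 says "If feasible, CYP2A6 will be analyzed in natural scale", yet cites the logged code with no exception.

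**Size if the listed terms are followed.** The plan states no figure to reproduce. Inputs:
- 80 and 40 randomized, with at least 50% of the CHTP 1.2 arm assumed to stay in the ambulatory per-protocol set (SAP 8), so 0.5 x 80 = 40 at Day 90.
- Two-sided 95% intervals (SAP 12.1.8).
- rho, the baseline to follow-up correlation given sex and CC stratum: assumed, because the documents give none.

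The SE without baseline relative to with baseline is 1/sqrt(1-rho^2). The 95% half-width in SD units is t(N-4) x sqrt(1/n1+1/n2) without baseline, and t(N-5) x sqrt(1/n1+1/n2) x sqrt(1-rho^2) with it. The value of sqrt(1/n1+1/n2) is 0.1936 for 80 vs 40, 0.2236 for 40 vs 40, and 0.2297 for 40 vs 36 (an assumed 10% loss in the CC arm).

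| | No baseline | rho 0.3 | 0.5 | 0.7 | 0.8 | 0.9 |
|---|---|---|---|---|---|---|
| SE ratio | – | 1.048 | 1.155 | 1.400 | 1.667 | 2.294 |
| Half-width, Day 5/6, 80 vs 40 | 0.384 | 0.366 | 0.332 | 0.274 | 0.230 | 0.167 |
| Half-width, Day 90, 40 vs 40 | 0.445 | 0.425 | 0.386 | 0.318 | 0.267 | 0.194 |
| Half-width, Day 90, 40 vs 36 | 0.458 | 0.437 | 0.397 | 0.327 | 0.275 | 0.200 |

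The low end cannot be ruled out for spirometry. Screening is measured at least 1 hour after smoking and up to 42 days before Admission (Protocol 9.1), while Day 6 and Day 90 are measured before any smoking.

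**Point estimate.** A baseline imbalance of d SD among analysed subjects shifts the unadjusted difference by rho x d. As an illustration only, d = 0.2 gives 0.06, 0.10, 0.14 and 0.18 SD at rho 0.3, 0.5, 0.7 and 0.9. Adjustment removes that measured part and nothing else.

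**The case against.** The strongest reply is that the SAP has nearly resolved this itself. A model statement adopted with one named exception is more specific than a prose list, dropping baseline is not that exception, and the parallel sections agree. On that reading this is an editorial slip with no effect on results. Neither endpoint is confirmatory, carries multiplicity control or supports the sample size, and with the arms as randomized both models are unbiased.

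Most of that stands, and it is why the point is minor. It does not remove the conflict. In the QSU-brief and CYP2A6 sections the prose is clear and the code pointer is the faulty part, so a reader could equally conclude that prose governs here.

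Three further points on that side are right. SAP section 9 lists changes from the protocol, and the protocol has no model for these endpoints, so its silence is no evidence either way. The SE range says little beyond its dependence on rho. The Day 90 imbalance illustration arises from per-protocol selection on CC use after randomization (SAP 11.1, Table 12), a separate issue that baseline adjustment does not cure.

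**Conclusion.** The concern holds: two sections each specify two models, and the SAP does not choose between them. That rests on the text alone and is certain. Any effect on results is conditional. It is zero if the cited code is run, which is the likelier intention. If the listed terms are followed, the SE is 5% to 129% larger for assumed rho between 0.3 and 0.9; at rho 0.7 with 40 vs 40, the half-width is 0.445 SD instead of 0.318. These figures assume balanced strata and the subject numbers shown. Primary endpoints, alpha and sample size are unaffected. It is a low-severity point worth correcting because the correction is so cheap.

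**What to change.** In SAP 12.5.2.3 and 12.5.2.4, add the untransformed baseline value to the listed terms, so that text and code both read `Value = baseline sex cigarette_cons arm`. State that baseline is Day -1 for CYP1A2 and Screening for spirometry. This follows from Table 17 but is better made explicit. For spirometry, pair pre- with pre-bronchodilator and post- with post-bronchodilator values. Also reconcile this with Protocol 7.3.10.1, which describes change after Screening from pre-bronchodilator values, whereas the endpoint in Protocol 3.2 covers both. If the sponsor really means to omit baseline, the SAP should say so as a second exception to the cited code.

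The cost is a couple of words in each term list plus a short sentence on baseline, no new data, and one degree of freedom per model. For CYP1A2, subjects without a valid baseline ratio drop out: the ratio is not calculated when either analyte is below quantification (SAP 7.1.3), values soon after an interfering medication are invalid (SAP 11.4), and missing laboratory baselines are not imputed (SAP 12.1.5). That loss is already in the plan if the cited code is the plan. On precision, adjustment still wins while the missing share f satisfies (1-rho^2)/(1-f) < 1, that is f < rho^2: 9%, 25% and 49% at rho 0.3, 0.5 and 0.7. For spirometry little or no loss is expected, because the Screening test decides eligibility (Protocol 7.3.10.1).
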